4.5.2.4. Clinical Endpoints based on Time and Events

Definitions of cumulative incidence of event efficacy endpoints and censoring rules are given in [Table 7](#).

Table 7: Cumulative Incidence of Event Endpoints - Definitions of Events and Censoring Rules

Endpoint	Event and Time	Censor and Time	Observation Period
Cumulative Incidence of Death	Event = patient died Time is days since first dose date, i.e., (Date of death – Date of first dose)	Censor = patient is alive Time is days alive = (last follow-up date – Date of first dose)	day 1 through day 169 (Phase 1 patients only) day 1 through day 57 (Phase 2/3 patients)
Cumulative Incidence of Mechanical Ventilation	Event = patient ever went on mechanical ventilation Time is days since first dose date until first event of ventilation, i.e., (Date of first mechanical ventilation – Date of first dose)	Censor otherwise (even if never ventilated and died) Time is days since first dose until last follow-up = (last follow-up date – Date of first dose)	day 1 through day 29
Cumulative Incidence of Death or Mechanical Ventilation	Event = patient died or patient ever went on mechanical ventilation Time is days since first dose date until the death date or the earliest date of the ordinal scale reaching 2, whichever is earlier, i.e. (min (Death Date, Date of first mechanical ventilation) – Date of first dose))	Censor otherwise The censor date is the last follow-up date. Time is days since first dose until last follow-up = (last follow-up date – Date of first dose)	day 1 through day 29

Endpoint	Event and Time	Censor and Time	Observation Period
Time to Discharge	Event = First discharge and alive Time is days since first dose date until first discharge, i.e., (Date of first discharge – Date of first dose)	Censor otherwise If alive, then Time = (End of study date – Date of first dose) If died, then Time = 168 days for Phase 1 patients or 56 days for Phase 2/3 patients	day 1 through day 169 (Phase 1 patients) day 1 through day 57 (Phase 2/3 patients)

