4.5.2.2. Secondary Clinical Efficacy Endpoint

The secondary clinical efficacy endpoints and populations are defined in [Table 5](#). All clinical outcomes derived from the ordinal scale (Section [4.5.1.2](#)) will be based on data until day 29.

Definition of readmission

Readmission to hospital will also be based on what investigators report on *Hospital – ICU Admission and Discharge CRF*.

Table 5: Secondary Clinical Efficacy Endpoints and Populations

Endpoint	Timepoint	Population
Proportion of patients who went on mechanical ventilation (for cohort 1 and cohort 1A)	By day 29	1. High viral load mFAS, 2. Seronegative mFAS, 3. mFAS;
Proportion of patients who died	
 • day 6 to day 29 • day 1 to day 29 	
Proportion of patients who were discharged	By day 29	
Proportion of patients who died or were readmitted	All available follow-up data	
Cumulative incidence of Death (i.e. Overall Survival)	All available follow-up data	
Cumulative incidence of Mechanical Ventilation (for cohort 1 and cohort 1A)	All available follow-up data up to day 29	
Cumulative incidence of Death or Mechanical Ventilation (for cohort 1 and cohort 1A)	All available follow-up data up to day 29	
Time to Discharge	All available follow-up data	

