4.5.2.3. Clinical Endpoints based on Proportions

Clinical endpoints based on proportions will be computed as numerator over denominator as given in [Table 6](#).

Table 6: Secondary Clinical Endpoints based on Proportions of Patients with Outcome

Number	Endpoint	Timepoint	Numerator	Denominator
1.	Died	day 6 to day X	Total number of patients who died after day 5 and on or before day X (death data will be captured from any CRF in the study)	Number of patients in the treatment group excluding patients who died or dropped out before day 6

		day 1 to day X	Total number of patients who died on or before day X (death data will be captured from any CRF in the study)	Number of patients in the treatment group
2.	Went on Mechanical Ventilation	Through day X	Number of patients who ever went on mechanical ventilation or ECMO (ordinal scale =2) through day X	Number of patients in the treatment group
3.	Discharge	Through day X	Number of patients who discharged through day X	Number of patients in the treatment group
4	Death or readmission	Through end of study	Number of patients who died or readmitted into hospital during the study	Number of patients in the treatment group

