5.6.2. Descriptive Analysis of Secondary Efficacy Endpoints

All analyses for the secondary efficacy endpoints are descriptive and all p-values are nominal.

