5.6.2.2. Descriptive Analysis of Secondary Clinical Efficacy Endpoints

All clinical endpoints based on proportions (defined in Section 4.5.2.3) will be analyzed using similar methods as for the primary clinical efficacy endpoint described in Section 5.6.1.2. The analysis will be performed for patients by baseline viral load ($\leq 10^6$ vs $> 10^6$ copies/mL) in the mFAS, by serostatus in the mFAS, and in overall mFAS.

All clinical endpoints based on time-to-event (defined in Section 4.5.2.4) will be estimated using the Kaplan-Meier method and comparisons between treatment groups will be made using the stratified log-rank test with the type of background standard-of-care as stratification factor. P-values will be compared with 0.05 (two-sided).

The log-rank “observed minus expected” statistic (and its variance) will be used to calculate the one-step estimate of the event rate ratio and confidence interval for each pairwise comparison versus placebo group (Peto 1977) [2].

As sensitivity analysis, the hazard ratio and its 95% CI will be estimated by the Cox proportional-hazards regression model with terms for treatment group, and type of background standard-of-care. P values from the stratified log-rank test will be reported. Hazard ratio (HR) < 1 will imply reduction of hazard of REGN10933+REGN10987 versus placebo. Estimates of median times along with 25th and 75th percentiles (if median and quartiles are reached) and associated two-sided 95% CI will be reported using the Kaplan-Meier method.

Landmark analysis starting from day 6 will be performed using similar Cox proportional-hazard model on the cumulative incidence of death or mechanical ventilation and cumulative incidence of death. The patients with corresponding events occurring before day 6 and patients who drop out early from study before day 6 will be excluded from the analysis (Dafni, U. 2011) [3]. The analysis will be performed for patients by baseline viral load ($\leq 10^6$ vs $> 10^6$ copies/mL) in mFAS (with baseline serostatus added to the stratified log-rank test and the Cox model as a factor), by serostatus in mFAS, and overall mFAS (with baseline serostatus added to the stratified log-rank test and the Cox model as a factor).

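### Kaplan-Meier with unventilated deaths censored slightly overstates the cumulative incidence of mechanical ventilation, a secondary endpoint

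*SAP*

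**What the plan says.** SAP 4.5.2.4, Table 7, defines the event as first mechanical ventilation, observed from day 1 through day 29. For everyone else the rule is "Censor otherwise (even if never ventilated and died". The censoring time is given as "Time is days since first dose until last follow-up = (last follow-up date – Date of first dose". Table 7 does not say what the last follow-up date is for a patient who has died.

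SAP 5.6.2.2 says that all endpoints in that section "will be estimated using the Kaplan-Meier method and comparisons between treatment groups will be made using the stratified log-rank test". It adds a one-step event rate ratio from the log-rank statistic, and then: "As sensitivity analysis, the hazard ratio and its 95% CI will be estimated by the Cox proportional-hazards regression model". Neither document names an estimator that treats death as a competing event.

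Three neighbouring provisions bear on the point:

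- SAP Table 6 also plans a simple proportion ventilated. Its numerator is "Number of patients who ever went on mechanical ventilation or ECMO (ordinal scale =2) through day X" and its denominator is every patient in the treatment group, so deaths stay in the denominator.
- For time to discharge, Table 7 gives a specific time for deaths: "If died, then Time = 168 days for Phase 1 patients or 56 days for Phase 2/3 patients".
- SAP 5.6.2 sets the status of the endpoint: "All analyses for the secondary efficacy endpoints are descriptive and all p-values are nominal".

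**The concern.** Kaplan-Meier treats a censored patient as someone who could still have the event later, at the same rate as those who remain under observation. That is reasonable for a patient lost to follow-up. It is not true of a patient who has died. Censoring at death passes that patient's weight to the survivors, so each later ventilation moves the curve by too much. The result is not the proportion of patients ventilated by a given day, which is what the endpoint's name promises. It exceeds that proportion whenever an unventilated death precedes a later ventilation in the same arm.

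What is at stake is the accuracy of a reported absolute incidence. Even with complete follow-up, the Table 7 curve at day 29 would not match the Table 6 proportion for the same arm, and the report would carry two different figures under similar names.

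**Working it through.** The plan states no figure for ventilation incidence, so there is none to reproduce. The check is an illustration built on the composite rates that the documents do give.

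**Inputs**

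- F, the proportion with death or ventilation by day 29. The main case is 13.1% (SAP 2.3; protocol 11.2.3), the assumed placebo rate, taken from the blinded seronegative mFAS in the pooled cohorts. The high case is 25% (protocol 11.2.2), the placebo rate assumed for seronegative cohort 1 patients in phase 1/2.
- s, the share of first events that are deaths without ventilation. The documents do not give it. It is assumed to lie between 10% and 75%.

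**Formulas**

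- True incidence of ventilation (Aalen-Johansen): (1 − s)F.
- 1-KM with deaths censored at death, constant cause-specific hazards: 1 − (1 − F)^(1 − s).
- Upper bound for 1-KM, all deaths before any ventilation: (1 − s)F / (1 − sF).

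**One case in full, F = 13.1%, s = 50%**

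- True incidence: 0.5 × 0.131 = 6.55%.
- 1-KM: 1 − 0.869^0.5 = 6.78%, an excess of 0.23 points.
- Upper bound: 0.0655 / 0.9345 = 7.01%, an excess of 0.46 points.

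**All cases** (excess in percentage points, from unrounded values)

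| F | s | True | 1-KM, constant hazards | Excess | 1-KM, deaths first | Excess |
|---|---|---|---|---|---|---|
| 13.1% | 10% | 11.79% | 11.87% | 0.08 | 11.95% | 0.16 |
| 13.1% | 25% | 9.83% | 10.00% | 0.17 | 10.16% | 0.33 |
| 13.1% | 50% | 6.55% | 6.78% | 0.23 | 7.01% | 0.46 |
| 13.1% | 75% | 3.28% | 3.45% | 0.17 | 3.63% | 0.36 |
| 25% | 10% | 22.50% | 22.81% | 0.31 | 23.08% | 0.58 |
| 25% | 25% | 18.75% | 19.41% | 0.66 | 20.00% | 1.25 |
| 25% | 50% | 12.50% | 13.40% | 0.90 | 14.29% | 1.79 |
| 25% | 75% | 6.25% | 6.94% | 0.69 | 7.69% | 1.44 |

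**Simulation check.** With 1,000,000 patients, F = 13.1% and s = 50%, 1-KM with deaths censored at death is 6.82% and the simple proportion is 6.59%. Carrying unventilated deaths event-free to the end of the window also gives 6.59%. With complete follow-up, that rule and the simple proportion agree.

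**What the log-rank test and the curve each measure.** Take F = 13.1% and s = 50% on placebo, so that each cause-specific cumulative hazard is 0.5 × −ln(0.869) = 0.0702. Let the drug halve the hazard of unventilated death and leave the ventilation hazard alone.

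- 1-KM is 1 − exp(−0.0702) = 6.78% in both arms.
- True incidence is 6.55% on placebo. On drug it is 0.0702 / (0.0702 + 0.0351) × (1 − exp(−0.1053)) = 6.66%.

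The log-rank test is correctly null here, because the ventilation hazard is the same in both arms. The incidence differs slightly because more patients on drug survive to be ventilated.

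**The case against.** The strongest reply is that little depends on this curve. The endpoint is secondary and descriptive, and ventilation alone appears nowhere in the seven-step hierarchy of SAP 5.6.3. The primary composite counts deaths as events. Table 6 already gives the proportion ventilated over all patients, and death is reported separately, so a reader can see the components side by side. All of this stands. It limits the importance of the point but does not correct the curve.

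The censoring date is also open to reading. If the last follow-up date for a dead patient meant the end of the day-29 window, the bias would disappear. Table 7 does not say so, although it states a fixed time for deaths under discharge. The date of death is the natural reading.

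A reader might go further in two ways that the documents do not support.

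- One might infer that the comparison of the arms is distorted. It is not. With deaths censored, the log-rank test and the Cox model validly compare cause-specific hazards. They simply do not compare cumulative incidences.
- One might infer that the discharge rule proves the table inconsistent. It does not. Discharge is a good outcome, so holding deaths as never discharged scores death as failure. The same rule for ventilation would score an unventilated death as event-free. Different handling is not in itself an error, and the explicit parenthesis suggests a deliberate choice.

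Finally, not all disagreement with Table 6 comes from deaths. Table 6 counts missing data as non-events, whereas Kaplan-Meier and Aalen-Johansen both censor dropouts. Some gap would remain after the change.

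**Conclusion.** The point holds for the absolute incidence curve and no further. With deaths censored at death, 1-KM overstates the incidence of mechanical ventilation. The direction is certain if any unventilated death precedes a later ventilation in the arm.

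The size is modest. At the 13.1% composite rate the excess is about 0.1 to 0.2 percentage points under constant hazards and at most about 0.5. At 25% it is about 0.3 to 0.9 points and at most about 1.8. These figures rest on the assumed 10% to 75% share of unventilated deaths and on censoring at the date of death.

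No confirmatory result is affected. The material does not support a claim that the treatment comparison is biased, or that the discharge rule alone shows an error.

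**What to change.** In SAP 5.6.2.2, estimate the cumulative incidence of mechanical ventilation by Aalen-Johansen, with death without ventilation as a competing event. With complete follow-up, carrying unventilated deaths event-free to day 29 gives the same result. In Table 7, state how patients who die unventilated are handled and on what date, so that the last follow-up date is no longer left to interpretation.

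Keep the stratified log-rank test, the one-step rate ratio and the Cox model for this endpoint, and label them as comparisons of cause-specific hazards. Gray's test may be added, but it is optional: it compares cumulative incidences, which is a different question.

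The cost is a few lines of SAP text and a standard option in the planned SAS software (an event code for the competing-risk curve). No new data are needed.

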4.5.3. Exploratory Endpoints

The exploratory endpoints include:

- Proportion of patients with treatment failure having mutations in the gene encoding the SARS-CoV-2 S protein through day 29
- Change and percentage change in neutrophil-lymphocyte ratio (NLR) at each visit through day 29
- Change and percentage change in D-dimer at each visit through day 29
- Change and percentage change in ferritin at each visit through day 29
- Change and percentage change in C-reactive protein (CRP) at each visit through day 29
- Change and percentage change in lactate dehydrogenase (LDH) at each visit through day 29

4.6. Safety Variables

4.6.1. Adverse Events and Serious Adverse Events

Treatment-emergent adverse events (AEs) (grade 3 or 4; for phase 1 only), treatment-emergent serious adverse events (SAEs) and treatment-emergent adverse events of special interest (AESIs) will be collected according to the Schedule of Events (Appendix 10.1 and Appendix 10.2). All adverse events are to be coded using the Medical Dictionary for Regulatory Activities (MedDRA).

Treatment-emergent adverse events are defined as those that are not present at baseline or represent the exacerbation of a pre-existing condition.

Infusion-related reactions are defined as any relevant adverse event that occurs during the infusion or up to day 4.

Hypersensitivity reactions are defined as any relevant adverse event that occurs during the infusion or up to study day 29.

The severity of adverse events (including test findings classified as adverse events) will be graded using the current version of the NCI-CTCAE v5.0 (Division of Cancer Treatment and Diagnosis [DCTD], 2020).

Treatment-emergent AEs, treatment-emergent SAEs, or treatment-emergent AESIs not listed in the NCI-CTCAE will be graded according to the scale in [Table 8](#).

Table 8: NCI-CTCAE Severity Grading System for Adverse Events

Grade	Severity	Description
1	Mild	Asymptomatic or mild symptoms; clinical or diagnostic observations only; intervention not indicated
2	Moderate	Minimal, local, or noninvasive intervention indicated; limiting age appropriate instrumental activities of daily living (ADL)*
3	Severe	Severe or medically significant but not immediately life threatening; hospitalization or prolongation of hospitalization indicated; disabling; limiting self-care ADL†
4	Life-threatening	Life threatening consequences; urgent intervention indicated
5	Death	Death related to adverse events

*Instrumental ADL refers to preparing meals, shopping for groceries or clothes, using the telephone, managing money, etc.

† Self-care ADL refers to bathing, dressing, and undressing, feeding self, using the toilet, taking medications, and not bedridden.

4.6.2. Adverse Events of Special Interest

Adverse events of special interest (AESI) are AEs (serious or non-serious) of scientific and medical interest specific to this drug program, for which ongoing monitoring and rapid communication by the investigator to the sponsor will be done.

In this study, the AESIs are listed below:

- Grade ≥ 2 infusion related reactions
 - selected from Adverse Events CRF
- Grade ≥ 2 hypersensitivity reactions
 - selected from Adverse Events CRF

4.6.3. Laboratory Safety Variables

Blood Chemistry

Samples for laboratory testing will be collected at visits according to the schedule of events in Section [10.2](#).

Tests will include:

Sodium	Blood urea nitrogen (BUN)	Alkaline phosphatase
Potassium	Aspartate aminotransferase (AST)	Creatinine
Chloride	Alanine aminotransferase (ALT)	Creatine phosphokinase (CPK)
Carbon dioxide	Total bilirubin	Lactate dehydrogenase (LDH)
Glucose	Albumin	C-reactive protein (CRP)
Ferritin		

Hematology

Hematology, urinalysis, and pregnancy testing samples will be analyzed by the local laboratory.

Tests will include:

Hemoglobin	Differential:
Hematocrit	Neutrophils
Red blood cells (RBCs)	Lymphocytes
White blood cells (WBCs)	Monocytes
Platelet count	Basophils
	Eosinophils

Other Laboratory Tests

Coagulation tests: D-dimer, prothrombin time (PT/INR), activated partial thromboplastin time (aPTT).

Laboratory results, vital signs, and other diagnostic results or findings that are appraised by the investigator and determined by investigator to fulfil the criteria of TEAEs (grade 3 or 4), treatment-emergent SAEs, or treatment-emergent AESIs will be reported.

4.6.4. Vital Signs

Vital signs, including temperature, blood pressure, pulse, pulse oximetry and respiratory rate are recorded according to Schedule of Events table (See Section 10.2).

Body weight and height are recorded according to Schedule of Events table (See Section 10.2).

Supplemental oxygen/FiO₂ use will be measured at baseline to monitor the patient's status regarding gas exchange. As applicable, the following will be recorded:

- Oxygen flow rate in L/min (if not mechanically ventilated)
- FiO₂ (if mechanically ventilated)
- Resting SpO₂ (in %)

4.7. Pharmacokinetic Variables

The PK variable is the concentration of REGN10933 and REGN10987 antibodies in serum and sampling time that a sample was collected as specified in the Schedule of Events table (See Section 10.2).

4.8. Immunogenicity Variables

The immunogenicity variables are ADA and (in phase 2 and phase 3 only) NAb status, titer, and time-point/visit. Serum samples for ADA will be collected at the visits as specified in Section 10.2. Samples positive in the ADA assay will be further characterized for ADA titers and for the presence of NAb.

5. STATISTICAL METHODS

For continuous variables, descriptive statistics will include the following: the number of patients reflected in the calculation (n), mean, Q1, median, Q3, standard deviation (sd), minimum, and maximum.

For categorical or ordinal data, frequencies and percentages will be displayed for each category.

5.1. Demographics and Baseline Characteristics

Demographic and baseline characteristics variables given in Section 4.1 will be summarized by treatment group, and all groups combined. These will be analyzed for FAS and mFAS populations. Similar analysis will be performed by baseline serostatus and baseline viral load categories ($\leq 10^6$ copies/mL and $>10^6$ copies/mL) for mFAS population.

5.2. Medical History

Medical history will be summarized by SOC (system organ class) and PT (preferred term) and by treatment group and all groups combined in the mFAS and FAS population.

5.3. Prior / Concomitant Medications or Procedures

Prior or concomitant medications/procedures will be summarized by treatment groups. Summaries will present patient counts (and percentages) for all medications, dictionary coded by WHODRUG, by decreasing frequency of the overall group incidence (or high dose group incidence in tables where the overall is not presented) of ATC followed by ATC level 2, ATC level 4 and preferred term. Focus of the results will be on the list of targeted medications (Section 4.3) in the FAS and mFAS populations.

Number and proportion of patients undergoing a prior/concomitant procedure(s) will be summarized, sorted by decreasing frequency of SOC and PT based on the incidence in the overall group incidence (or high dose group incidence in tables where the overall is not presented). Patients will be counted only once for each SOC and PT linked to the procedure.

Prior or concomitant medications/procedures of interest for COVID-19 will be summarized similarly.

5.4. Subject Disposition

The following summaries will be provided for both mFAS and FAS populations.

- The total number of randomized patients: received a randomization number
- The total number of randomized patients who were not treated by study drug
- The total number of randomized patients who discontinued the study, and the reasons for discontinuation
- A summary of analysis sets including FAS, mFAS, SAF, PK, immunogenicity (ADA), and NAb analysis set (NAS) (Section 3).

5.5. Extent of Study Treatment Exposure

5.5.1. Exposure to Investigational Product

Exposure to study drug will be examined for each patient as recorded on the Study Drug Administration-IV CRF. The following variables will be analyzed by treatment group:

- Duration of intravenous infusion
- Total volume of drug administered (units: mL)
- Number of patients with total planned dose administered (yes/no)
 - If no, reason for not administration of total planned dose (equipment failure, adverse event, other)
- Number of patients with infusion interruptions (ie, patients completed the full dose but had infusion interruptions)
- Number of patients with infusion discontinuation (ie, patients didn't completed the full dose infusion)

The number and percentage of patients randomized and exposed to double-blind study drug will be presented for each treatment group.

